15.7. Follow-up Visit Compliance

As part of the informed consent process, all reasonable efforts will be made to obtain complete data for all subjects according to the follow-up visit schedule. PI and research staff will be expected to maintain continuous and open communication with study subjects regarding their participation in this study.

Three attempts via telephone will be made to contact subjects who do not return for a study follow-up visit. If after three telephone attempts the subjects cannot be contacted, a certified letter should be sent by the PI or designated study coordinator to the subject's last known address. If possible, public records should be searched to ascertain survival status. If efforts to reach the subject are unsuccessful after three telephone contacts and a certified letter, and there is no evidence of subject expiration, or the site has not been notified of a subject's wish to withdraw consent, a protocol deviation for a visit not done must be documented in the subject's source records and reported in the EDC system. A detailed record of all contact attempts should be maintained in the subject's file. This process should be repeated for all subsequently missed follow-up visits and documented accordingly. After required contact attempts are unsuccessful for at least 2 consecutive missed follow-up visits and the 12-month visit window (or any later subsequent visit window) has passed, only then should a subject be considered lost-to-follow-up (LTFU) and exited from the study.

In the event of a public health crisis, a global pandemic, a natural disaster, or any other event which would preclude research sites from conducting research or restrict subjects' ability to attend follow-up visits, guidance will be provided by the Sponsor and may include performing follow-up visits via alternative methods, extending visit windows, etc.

15.8. Subject Discontinuation and Replacement

A subject may discontinue participation at any time without penalty or loss of benefits to which the subject is otherwise entitled. In addition, a subject may be discontinued if in the PI's opinion it is in the subject's best interest. If a subject prematurely discontinues from the study, the reason will be recorded in the eCRF with supporting documentation. These results will be tabulated by number and percent for each category for discontinuation.

Subjects who prematurely exit the study after treatment will have their data maintained and evaluated up until the time of withdrawal. Subjects who are voluntarily or involuntarily (per PI discretion or if LTFU) withdrawn cannot re-enter the study. These subjects will not be replaced. There is no follow-up or observation planned for subjects who withdraw voluntarily or who are involuntarily withdrawn by the PI.

16. RISK/BENEFIT ASSESSMENT

16.1. Risks

The use of the DUO Venous Stent System in treating venous obstructions may result in anticipated potential risks or complications similar to other available endovascular implant devices (such as stents) used in these procedures. Such risks are included in the DUO Venous Stent System IFU and are listed below:

- Access failure or abrupt closure
- Allergic/anaphylactoid reaction to anticoagulant and/or antithrombotic therapy or contrast medium
- Allergic reaction to Nitinol
- Amputation
- Aneurysm
- Angina/coronary ischemia/myocardial infarction
- Arrhythmia
- Arteriovenous fistula
- Death
- Embolism
- Emergent repeat hospital intervention
- Extravasation
- Fever
- Gastrointestinal bleed from anticoagulation/antiplatelet medication
- Hematoma/hemorrhage
- Hypotension/hypertension
- Incorrect positioning of the stent requiring further stenting or surgery
- Intimal Injury/dissection
- Ischemia/infarction or tissue/organ
- Infection/abscess at insertion site
- Inflammation
- Malposition of stent
- Multi-organ failure
- Open surgical repair
- Pain
- Pulmonary Embolism
- Pseudoaneurysm
- Renal insufficiency or failure
- Respiratory distress or failure
- Restenosis
- Rupture
- Septicemia/bacteremia (sepsis)
- Stent implant fracture
- Stent implant migration (device moves over time)
- Trauma to adjacent structures

- Vasospasm
- Venous occlusion/thrombosis, remote from puncture site
- Venous occlusion/thrombosis, near puncture site
- Venous occlusion/restenosis of the treated vessel

These risks are present in any endovascular treatment procedure for which the study subjects would be indicated because of their disease and will be reviewed with all subjects during the informed consent process.

16.2. **Potential Benefits**

- The DUO Stent may help improve the blood flow in the leg vein.
- Participation in this study may yield information that is necessary for the development of better or new treatments for this disease and may benefit other people who have the same blockages in the leg veins.

16.3. **Justification for Clinical Trial**

The safety of the DUO Venous Stent System has been established through extensive design verification testing, including animal testing, and through a detailed risk analysis process per ISO 14971. The results of non-clinical testing have demonstrated safety and therefore it is anticipated that the assessment of risk and benefit is appropriate for the intended use of the study device and the initiation of this study.

This study is being conducted in to collect safety and efficacy data on the DUO Venous Stent System to support an FDA Premarket Approval application. All efforts will be made to minimize the occurrence of risk to study subjects through PI/institution qualification, PI training on the safe and proper use of the device in accordance with the IFU, PI/site training on the protocol, and clearly defining subject eligibility requirements (inclusion/exclusion criteria) and contraindications as described in the IFU.

17. SAFETY EVENTS AND REPORTING REQUIREMENTS

The PI at each participating site is ultimately responsible for the timely review and reporting of AEs per respective IRB/EC policy and in accordance with FDA and ISO 14155 (OUS sites) requirements.

The safety reporting period will begin at the time of enrollment into the study (See **Section 13.3.1** for details on what constitutes subject enrollment) and will continue through study completion.

All protocol reportable AEs will be monitored from the time of enrollment through the follow-up period for this study. A description of the event, including the start date, resolution (or date of final outcome assessment) date, action taken, and the outcome should be provided, along with the PI's assessment of the relationship between the event and the study device or study device procedure. Pain, neurological status, and functional impairment should be considered AEs when a subject's complaint of any of these symptoms is outside the normal pattern for the illness treated.

All protocol-reportable events reported during the safety observation period described above should be followed until the event is resolved or judged to be chronically stable. Follow-up information will be submitted to the Medical Monitor and/or the Sponsor as it becomes available.

In the event that the subject undergoes a SARS-CoV-2 test within 8 days of the index procedure and there is a delay in obtaining test results the subject may still be enrolled if they meet all of the other SARS-CoV-2 inclusion criteria, including successful completion of a COVID-19 questionnaire. If, when test results are received, the test result is positive, this must be recorded as an adverse event. **This is the only adverse event that will be captured prior to enrollment, as the start date of the adverse event will be the date of the SARS-CoV-2 testing, which occurred before the subject was enrolled.**

The Sponsor or its designee will include relevant adverse event information in annual Investigational Device Exemption (IDE) progress reports. Additionally, the Sponsor or its designee will report all applicable serious adverse events as vigilance reports per MEDDEV 2.12.1, Rev 8 (2013) "Guidelines on a Medical Devices Vigilance System" and as clinical trial reportable events per MEDDEV 2.7/3 "Clinical Investigations: Serious Adverse Event Reporting". The Sponsor will determine whether all the local PIs need to be informed immediately of a serious adverse event (SAE) or unanticipated adverse device effect (UADE), or whether this can be postponed until the next regularly scheduled study update.

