6.3. Observational Endpoints

- Device Success defined as:
 - Successful deployment of the DUO stent(s) at the intended target site, AND
 - Successful withdrawal of the delivery catheter(s) from the introducer sheath, AND
 - The DUO Stent remaining at the intended deployment location through completion of the index procedure as determined by the Principal Investigator (PI)
- Lesion success defined as target lesion patency of $\leq 50\%$ residual diameter or area stenosis of the stented segment at the completion of the procedure*
- Procedural success defined as lesion success without the occurrence of CEC adjudicated major adverse events (MAEs) from the time start of the index procedure through discharge*
- Stent fracture via X-ray through 36 months*
- Stent migration via X-ray through 36 months*
- Stent embolization via X-ray or venogram through 36 months*
- Primary patency of the stented segment via DUS at 24 and 36 months. If DUS shows $>50\%$ stenosis or occlusion, confirmation by diagnostic IVUS may be required.*
- Primary assisted patency of the stented segment via DUS at 24 and 36 months. If DUS shows $>50\%$ stenosis or occlusion, confirmation by diagnostic IVUS may be required.*
- Secondary patency of the stented segment via DUS at 24 and 36 months. If DUS shows $>50\%$ stenosis or occlusion, confirmation by diagnostic IVUS may be required.*
- Changes in the clinical CEAP Classification through 36 months
- Changes in the EQ-5D-3L through 36 months
- Changes in the Villalta Score through 36 months
- Changes in the VCSS Pain Score at 24 and 36 months
- Changes in the VEINES QOL/Sym Score through 36 months
- CEC adjudicated MAEs post 30 days through 36 months
- CEC adjudicated CD-TLR through 36 months
- CEC adjudicated CD-TVR through 36 months
- Venous Ulcer Assessment through 36 months

*Core Laboratory adjudicated

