10.2. Screening Success and Failure Criteria

Final eligibility of a subject will be confirmed during the Index Procedure. Subjects must provide prior informed consent no greater than 30 days prior to the index procedure. If 30 days have passed since the subject signed an informed consent form, the subject should be re-consented. Every effort will be made to ensure subject eligibility prior to enrollment. If the subject meets all the inclusion criteria and none of the exclusion criteria after pre-enrollment angioplasty, the subject will be considered eligible for

enrollment. If at any point prior to or just after pre-enrollment angioplasty, but prior to the DUO stent system being advanced through the introducer sheath, an exclusion criterion is met and/or an inclusion criterion is not met, the subject will be deemed a screen failure. No further follow-up will be required for these subjects; however, the following details will be documented in the subject's source records:

- Documentation that the subject is a screen failure
- Documentation of the inclusion/exclusion criteria that was met and/or not met, with clarification provided as necessary

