13.1.3. Baseline Venographic and IVUS Requirements

Baseline venographic and IVUS measurements of the target lesion and target vessels (visual estimate) shall be captured to determine eligibility and include, but are not limited to, the following:

- Target lesion(s) details including vessel location(s), lesion length(s), and pre-PTA % reduction in target vessel lumen diameter
- Indication for stenting and final disease state classification (acute DVT, nonthrombotic, chronic postthrombotic)
- Reference vessel diameter(s)

- Inflow venous patency (if patency of profunda cannot be confirmed by venogram or IVUS, pre-operative DUS findings may be used to confirm)
- Absence of thrombus and/or successfully treated thrombus for acute DVT subjects

13.2. **Pre-Dilation**

Please refer to the Instructions for Use (IFU) for detailed instructions regarding Pre-dilation inflation recommendations. It is recommended that pre-dilation equivalent to the size of the intended stent be performed.

Pre-dilation balloon-related details will be recorded and include, but are not limited to, the following: balloon name/manufacturer and balloon size, max pressure, inflation duration at max pressure, and max inflation diameter across all inflations.

13.3. **Study Device Treatment**

Subjects who meet all inclusion criteria, and who do not meet any exclusion criteria will be deemed eligible for Study Device Treatment.

13.3.1. **Enrollment (Intent-to-Treat)**

A subject is defined as intent-to-treat (ITT) and officially enrolled in the study once the DUO Venous Stent System is advanced through the introducer sheath.

Subjects in whom no DUO Stent implant is placed will be exited after 30 days. Subjects in whom at least one DUO Stent implant is placed will be followed for 36 months.

The per-protocol (PP) population will be defined as ITT subjects with evaluable data that have met the definition for device success, excluding subjects with major deviations, such as those who meet criteria for a protocol violation(s), as determined by the Sponsor.

13.3.2. **Treatment Recommendations**

Please refer to the IFU for detailed instructions regarding recommended criteria for use of the study device and stent sizing. IVUS is required for stent sizing.

NOTE: When overlapping study devices, there should be no more than 2mm of diameter difference between devices.

13.3.3. **Post-Study Device Treatment Measurements**

The following information should be recorded Post-Study Device Treatment:

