Index Procedure	The interventional procedure during which the study device is advanced through the introducer sheath and the subject is enrolled.
Intent-to-treat (ITT) subjects	A subject is defined as an ITT and officially enrolled in the study once the DUO Venous Stent System is advanced through the introducer sheath.
Lesion Success	Lesion success defined as target lesion patency of $\leq 50\%$ residual diameter or area stenosis of the stented segment at the completion of the procedure, as assessed by the core laboratory.
Major Amputation	Any above the ankle amputation to the target limb.
Myocardial Infarction (MI)	Q wave MI (QWMI): requires one of the following criteria:
	
 • Chest pain or other acute symptoms consistent with myocardial ischemia and new pathological Q waves in two or more contiguous ECG leads
	
 • New pathologic Q waves in two or more contiguous ECG leads and elevation of cardiac enzymes above normal.

Term	Definition
	
Non-Q Wave MI (NQWMI): defined as either: elevated CK = 2X the laboratory upper limit of normal with the presence of an elevated CK-MB (any amount above the laboratory upper limit of normal) in the absence of new pathological Q waves or elevated CK-MB = 3X the laboratory upper limit of normal in the absence of new pathological Q waves.

Per-protocol (PP) subjects	
The PP population will be defined as ITT subjects with evaluable data that have met the definition for device success, excluding subjects with major deviations, such as those who meet criteria for a protocol violation(s), as determined by the Sponsor.

Primary Assisted Patency	
Primary assisted patency at 12 months defined as freedom from DUS core laboratory adjudicated occlusion or stenosis >50% within the stented segment following a reintervention due to a >50% but <100% stenosis. If DUS shows >50% stenosis or occlusion, confirmation by diagnostic IVUS is required.

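### Adverse event capture starts when the DUO system enters the sheath, but the safety endpoint and procedural success cover the whole index procedure, so the windows must be reconciled

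*Combined protocol and SAP*

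**What the plan says.** **Capture rule (Section 17).** "The safety reporting period will begin at the time of enrollment into the study", and "All protocol reportable AEs will be monitored from the time of enrollment through the follow-up period for this study". One exception is named, a SARS-CoV-2 test whose positive result arrives late: "This is the only adverse event that will be captured prior to enrollment".

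**Moment of enrollment (Section 13.3.1, repeated in 19.2 and 23).** A subject is "officially enrolled in the study once the DUO Venous Stent System is advanced through the introducer sheath".

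**What comes before it.** Baseline venography and IVUS (13.1) and the recommended pre-dilation (13.2) are described ahead of device treatment. Section 10.2 says outright that angioplasty can come first: "If the subject meets all the inclusion criteria and none of the exclusion criteria after pre-enrollment angioplasty", the subject is eligible. A subject who fails a criterion at that stage is a screen failure, and "No further follow-up will be required for these subjects".

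**What the endpoint covers.** Section 6.1 includes device- or procedure-related bleeding and venous injury at the target vessel, target lesion or access site. Section 19.10 counts MAEs within 30 days of the index procedure, which Section 23 defines as "The interventional procedure during which the study device is advanced through the introducer sheath and the subject is enrolled".

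**Procedural success.** Section 6.3 counts "major adverse events (MAEs) from the time start of the index procedure through discharge". The glossary entry in Section 23 starts instead at the time of treatment.

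**Relatedness.** Section 17.1 grades AEs against the device or the study device procedure. Section 23 starts the study device procedure at the entry of the first DUO system, the same moment as enrollment.

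**The concern.** The capture rule and the endpoint do not share a start point. Venous access and balloon pre-dilation are steps at which an access-site bleed or a venous injury can happen, and both are named MAE components when they reach the stated threshold (intervention or, for bleeds, transfusion of at least 2 units). If sites follow Section 17 as written, such an event before device entry is not recorded as an AE, even when the subject is enrolled minutes later and analyzed in the safety population.

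Two things are at stake. First, the primary safety proportion can be too favorable against its own definition. An uncaptured event leaves the subject in the denominator and moves that subject into the event-free numerator, so the error runs in one direction only. Second, procedural success as worded in 6.3 cannot be computed in full from data collected under Section 17, and its two definitions differ. Sites may also settle the conflict differently, so that the same event counts at one center and not at another.

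**Working it through.** **Step 1: the windows side by side.**

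| Item | Start | Source |
|---|---|---|
| AE reporting and monitoring | DUO system enters sheath | 17, 13.3.1 |
| Study device procedure (relatedness) | DUO system enters sheath | 17.1, 23 |
| 30-day safety endpoint | Index procedure, the whole intervention | 19.10, 23 |
| Procedural success | Start of index procedure | 6.3 |
| Procedural success (glossary) | Time of treatment | 23 |

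The first two rows start later than the third and fourth. The gap contains access, imaging and pre-dilation. The glossary wording can be read either way.

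**Step 2: reproduce the plan's safety calculation.** Inputs from 19.10: exact one-sample binomial test, one-sided alpha 2.5%, performance goal 89%, assumed freedom 96.1%, 140 evaluable subjects. With X the number of subjects with an MAE, success requires X ≤ c, where c is the largest value with P(X ≤ c | n, 0.11) ≤ 0.025.

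- n = 140: P(X ≤ 8 | 140, 0.11) = 0.0240 and P(X ≤ 9 | 140, 0.11) = 0.0482, so c = 8.
- Power: P(X ≤ 8 | 140, 0.039) = 0.902, which agrees with the stated 90%.
- Enrollment: 140 / (1 − 0.125) = 160, as in 19.3.
- If all 160 were evaluable: P(X ≤ 9 | 160, 0.11) = 0.0145 and P(X ≤ 10 | 160, 0.11) = 0.0296, so c = 9.

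**Step 3: how thin the margin is.** With 140 evaluable, 8 MAEs pass (p = 0.024) and 9 fail (p = 0.048). With 160, 9 pass (p = 0.0145) and 10 fail (p = 0.030). At the limit, one uncaptured event changes the result.

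**Step 4: illustrate the effect on false success.** Suppose true freedom from MAE over the whole index procedure and 30 days is exactly 89%, and d is the absolute share of subjects whose only MAE falls before device entry and is not captured. The captured MAE rate is then 0.11 − d, and the false-success probability is P(X ≤ c | n, 0.11 − d). The documents give no value for d. The range below is an assumption; for scale, the first terms in the 19.10 sums, which appear to be the major-bleeding rates, run from 0.3% to 1.1%.

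| d (percentage points) | n = 140, c = 8 | n = 160, c = 9 |
|---|---|---|
| 0 | 2.40% | 1.45% |
| 0.25 | 2.94% | 1.83% |
| 0.5 | 3.59% | 2.30% |
| 1.0 | 5.29% | 3.59% |

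This treats the all-subjects comparison as a single test at one-sided 2.5% and leaves aside the Hochberg step with the SARS-CoV-2 negative subset.

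**The case against.** Several points on the other side stand.

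- **No endpoint text excludes these events.** A reader might infer that access and pre-dilation MAEs are outside the primary safety endpoint by definition. The documents do not say so. Sections 6.1, 19.10 and 23 read as covering the whole intervention, the schedule in 8.1 marks AE assessment at the index procedure, and 13.3.4 asks for adverse event occurrence to be recorded at its completion. But neither 8.1 nor 13.3.4 gives a start time, and Section 17 does. What the documents show is a conflict, not an exclusion.
- **Clot removal is partly covered by eligibility.** Inclusion criterion 16 requires freedom from bleeding and symptomatic PE after thrombus treatment and before any DUO stent, so DVT subjects with those events should not reach enrollment. Venous injuries, and bleeds from access or pre-dilation in other subjects, remain open.
- **Few components can be lost.** In an enrolled subject, death, stent embolization and thrombus within the stent cannot precede device entry. A reader might infer that peri-procedural deaths go uncounted; a death in an enrolled subject falls after enrollment and is captured. A condition that worsens after enrollment is recordable under 17.1, and a bleed that first shows after sheath removal may be captured too, although no onset rule is given.
- **The benchmark comparison is not available.** A reader might infer that the trial counts over a shorter window than the literature behind the 89% goal. Section 19.10 gives only rates and labels from the cited meta-analysis, not its event windows. The trial's MAE also adds components that are not in that sum, which pushes the other way. Net bias against the benchmark is not shown.
- **The CEC could look.** Section 21.7.2 allows review at the sponsor's request, and core laboratories see the index imaging. Neither is a stated route for events before enrollment.

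**Conclusion.** The capture rule in Section 17 conflicts with the trial's own windows for the 30-day safety endpoint and procedural success, and the passages must be reconciled. Applied literally, the rule can drop access or pre-dilation bleeds and venous injuries in subjects who are then enrolled. Any such loss biases freedom from MAE upward relative to the endpoint as defined. The conclusion goes no further: it does not rest on a comparison with the literature windows or on missed deaths.

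The size is unknown because the documents give no pre-entry event share. Over the assumed 0.25 to 1.0 point, false success stays below the nominal 2.5% in one setting (160 evaluable, up to 0.5 point) and reaches about twice nominal in another (140 evaluable, 1.0 point). These figures are illustrations. The firmer statement is that the pass limit is 8 or 9 events, so one unrecorded event can decide a close result. The matter should be corrected; it does not undermine the sample size or the test.

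**What to change.** For every subject who becomes enrolled, start AE and MAE capture at venous access of the index procedure. Use that single start in Section 17, in the 30-day safety endpoint (6.1 and 19.10) and in both definitions of procedural success (6.3 and Section 23). Grade the relatedness of MAEs against the index procedure, not only against the study device procedure that begins at device entry; otherwise an event may be recorded and still be classed as unrelated.

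Subjects who become screen failures after pre-enrollment angioplasty stay outside the ITT set. List separately any event in these consented subjects that would meet the MAE definition, so that cases stopped by a complication are visible.

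The cost is wording in a few sections, a few more AE forms and a possibly slightly higher observed MAE rate. The required 140 evaluable subjects, the performance goal and the test do not change.

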7.1. Anticipated Number of Subjects and Investigational Sites

Up to 160 subjects will be enrolled at up to 45 U.S. and International investigative sites. Each site can enroll a maximum of 32 subjects, establishing an enrollment cap at 20% of the total subject sample size.

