17.6.1. UADE Reporting

Any event that is suspected of meeting UADE criteria should be reported in the same manner as a SAE or SADE and must be reported by the PI (or designee) to the Sponsor ***within 2 business days (Monday through Friday) from first knowledge of event*** and must also be reported to the IRB/EC per the applicable reporting guidelines. All SAEs will be reviewed by the Sponsor (or designee) to determine if UADE criteria is met, and if so, the Sponsor or designee will immediately conduct an evaluation and report the results of the evaluation to FDA, all reviewing IRBs/ECs, and participating PIs within 10 business days after the Sponsor first receives notice of the UADE.

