Study close-out visits will be conducted after the final follow-up visit is completed at each site. Following the resolution of any outstanding data discrepancies and adverse events, the remaining study devices will be collected and returned to the Sponsor. A final study report will be generated and submitted to the PI and the appropriate study oversight authorities. Study document retention requirements will be reviewed with each site during the close-out visit.

21.4. **Device Accountability**

All study devices will be provided to the PI by the Sponsor after being tested, released, and shipped according to appropriate standards. The PI and/or designee is responsible for the secure storage of and controlled access to the study devices and accountability. The study device shall not be dispensed to any person who is not a consented study subject under this protocol.

21.5. **Investigator Reports**

21CFR Parts 50 & 56; ISO 14155:2011 Section 4

All PIs will be responsible for preparing and submitting the following complete, accurate, and timely reports:

To the Sponsor and the IRB/EC:

- Any unanticipated adverse device effect occurring during an investigation as soon as possible but no later than 2 business days after first learning of the effect.
- Assist Sponsor in generating progress reports on the investigation at regular intervals, but in no event less often than yearly. If there is a study monitor, a copy of the report will also be sent to the monitor.

- Any deviation from the investigational plan made to protect the life or physical well-being of a subject in an emergency, as soon as possible but no later than 5 working days after the emergency occurs. Except in emergency situations, a protocol deviation may require prior Sponsor approval. If the deviation may affect the scientific soundness of the plan or the rights, safety, or welfare of subjects, prior FDA and IRB/EC approvals are required.
- Any use of the device without obtaining informed consent must be reported within 5 working days after such use.
- Assist Sponsor in generating a final report within 3 months following termination or completion of the investigation or an individual PI's part of the investigation.
- Any further information requested by FDA or the IRB/EC about any aspect of the investigation.

To the Sponsor:

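### The Section 17 introduction lets the sponsor postpone telling investigators of a UADE until an undefined next update, a delay that Section 17.6.1 does not allow

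*Combined protocol and SAP*

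**What the plan says.** Two places in Section 17 govern when the sponsor tells investigators about a UADE.

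- **Section 17, introduction.** The sponsor decides if every local PI has to hear at once about an SAE or an "unanticipated adverse device effect (UADE), or whether this can be postponed until the next regularly scheduled study update". UADEs are named. No maximum delay is given, the update is not defined, and there is no reference to Section 17.6.1.
- **Section 17.6.1 (UADE Reporting).** "All SAEs will be reviewed by the Sponsor (or designee) to determine if UADE criteria is met". If they are met, the sponsor must evaluate the event immediately. Its further duty is to "report the results of the evaluation to FDA, all reviewing IRBs/ECs, and participating PIs within 10 business days after the Sponsor first receives notice". No discretion over timing is stated.

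The reporting site has its own deadline. Under Section 21.5 the PI reports a UADE to the sponsor and the IRB/EC "no later than 2 business days after first learning of the effect", and Section 17.6.1 sets the same 2-business-day limit for reporting to the sponsor. Neither duty tells the other sites anything.

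**The concern.** For a confirmed UADE the event, the sender and (reading local PIs and participating PIs as the same people) the recipients are identical in the two sections. One section gives an open-ended option and the other a fixed deadline. The introduction comes first and names UADEs, so someone working from it could hold back notice and believe the protocol allows it.

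What is at stake is investigator knowledge while the device is still being implanted. Section 4.2 describes this as the first investigation of the system in humans, and Section 7.1 states that "Up to 160 subjects will be enrolled at up to 45 U.S. and International investigative sites". By the definition in Section 17.6, a UADE is a serious effect not previously identified in nature, severity or degree of incidence. An investigator who has not been told of one cannot use it when consenting and treating the next subject. No endpoint, error rate or sample size is affected.

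**Working it through.** This is a comparison of texts. The plan states no figure to reproduce, and the only arithmetic is on reporting deadlines.

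**1. The two rules side by side, for a confirmed UADE**

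| | Section 17, introduction | Section 17.6.1 |
|---|---|---|
| Events | SAE or UADE | UADE |
| Who acts | Sponsor | Sponsor or designee |
| Who is told | All local PIs | FDA, all reviewing IRBs/ECs, participating PIs |
| What is sent | Notice of the event | Results of the evaluation |
| Latest time | Next scheduled update, interval undefined | 10 business days from sponsor notice |
| Discretion | Yes | None stated |

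**2. Maximum delay to the other PIs**

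- Under 17.6.1: 2 business days (site to sponsor) + 10 business days (sponsor to PIs) = 12 business days from when the reporting PI first learns of the event, if each deadline is met.
- Under the introduction: 2 business days + the time to the next update. The second term has no stated bound.

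**3. Size of the gap under assumed update intervals**

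The intervals below are assumptions, not figures from the protocol. A business year is taken as 52 × 5 = 260 days. The worst case is sponsor notice arriving just after an update. Excess = interval − 10.

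- Monthly: 260/12 ≈ 21.7 business days; excess about 11.7.
- Quarterly: 260/4 = 65 business days; excess 55.
- Yearly: 260 business days; excess 250.

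The excess is zero only if an update always falls within 10 business days of sponsor notice. Nothing in the protocol says that it does.

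**4. Does any other section supply the missing limit?**

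- Section 17.1 sends UADEs to the reporting requirements in the subsections that follow, but for events as evaluated by the PI. It does not limit the sponsor's choice in the introduction.
- Section 17.3.1 sets quarterly reports, to BfArM and not to sites.
- Section 21.5 has investigators help the sponsor produce "progress reports on the investigation at regular intervals, but in no event less often than yearly". Section 21.14 has the sponsor summarise progress reports sent to FDA and distribute them to sites. Neither is identified as the update meant in Section 17.
- Section 21.7.1 lets the DSMB choose which events need real-time reporting, and its recommendations go to the sponsor.
- Section 21.8 has the Medical Monitor review AEs for UADE potential and notify the sponsor.

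Only Section 17.6.1 sets a deadline by which all participating PIs must hear of a UADE.

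**The case against.** The strongest reply is that there is no true conflict. The introduction grants a permission and 17.6.1 imposes a duty. A sponsor that forgoes immediate notice but sends its evaluation by day 10 breaches neither. The two can also be read as covering different steps, first notice and then evaluation results, with the specific subsection governing the general introduction. This stands in part: a reader might infer that the two rules cannot both be followed, and that is too strong. But the introduction does not present 17.6.1 as its limit. The alternative it offers to immediate notice is the next update, with no cap.

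A second reply is that oversight continues. This also stands. The discretion covers only notice to local PIs, so the 10-business-day report to FDA and to every reviewing IRB/EC is untouched. The 2-business-day site report, the Medical Monitor and the DSMB reduce the risk further. It would be wrong to infer that a UADE could go unreported. What these safeguards do not guarantee is direct notice to the other implanting PIs.

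A reader might also take the yearly report as the update interval, or multiply an assumed enrolment rate by an assumed interval to count exposed subjects. The documents support neither. Quarterly and at-least-yearly reports both appear, and none is tied to the study update. No enrolment rate is given. The full 160 subjects could not be implanted after a UADE in any case, because the UADE must arise in someone already enrolled.

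**Conclusion.** The point holds as an internal inconsistency: the Section 17 introduction permits a delay in telling PIs of a UADE that Section 17.6.1 forbids. The stated limit is 10 business days in one place and absent in the other. The excess delays shown above depend entirely on assumed update intervals, and no count of subjects implanted in the gap can be given. Any harm would require open enrolment and a sponsor that relied on the introduction rather than on 17.6.1. For SAEs that are not UADEs the sections do not conflict. The wording should be corrected because it concerns a safety notice in a first-in-human, multi-site device trial and the correction is simple.

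**What to change.** Reconcile the two sections. In the introduction to Section 17, delete the mention of UADEs from the sentence that allows postponement, and add: *UADEs are reported to all participating PIs as stated in Section 17.6.1.* Leave the sponsor's discretion in place for SAEs that are not UADEs.

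The cost is one clause in a protocol amendment. It adds no reporting work, since Section 17.6.1 already requires the report, and it changes no analysis.
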